### a) Peripheral nerve disorders

Peripheral nerve disorders are frequently observed after treatment with Adcetris. If the event of peripheral nerve disorder becomes severe, it is difficult to continue treatment with Adcetris. It is important to control the onset of the event to allow for continuation of treatment (including dose reduction and restart of treatment after treatment interruption). Therefore, the profile of peripheral nerve disorders in Japanese patients as an adverse event of particular interest will be determined (i.e., information useful for continuation of treatment with Adcetris, including risk factors, commonly reported time to onset, outcomes, and the status of treatment with Adcetris, will be collected).

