Patients with the onset of infection	Patients with adverse drug reactions that fall under the category of MedDRA SOC Code 10021881 (Infections and infestations)
Patients with the onset of bacterial infection	Patients with adverse drug reactions that fall under the category of MedDRA HLTG Code 10004018 (Bacterial infection), 10008555 (Chlamydial infection), 10028474 (Mycoplasma infection) or 10039135 (Rickettsia infection)
Patients with the onset of fungal infection	Patients with adverse drug reactions that fall under the category of MedDRA HLTG Code 10017528 (Fungal infection)

Term	Definition										
Patients with the onset of viral infection	Patients with adverse drug reactions that fall under the category of MedDRA HLG Code 10047438 (Viral infection)										
Age	
If the month and day of the initial dose of Adcetris is < the month and day of birth, the patient's age will be calculated using the following formula: Year of the initial dose of Adcetris – year of birth – 1.
 
If the month and day of the initial dose of Adcetris is ≥ the month and day of birth, the patient's age will be calculated using the following formula: Year of the initial dose of Adcetris – year of birth.
 
If the month and day of birth are unknown, they should be “January 1,” and if the day of birth is unknown, it should be the first day of the month.
 
If the day, month, and year of birth are unknown but the patient's age is known, the patient's age should be used as it is.
										
BMI	BMI should be calculated using the following formula: Weight (kg)/(0.0001 × height (cm) × height (cm)). The obtained value should be rounded off to one decimal place.										
Disease duration	
The disease duration should be calculated using the following formula: [“Date of the initial dose of Adcetris” – “date of diagnosis of Hodgkin's or anaplastic large-cell lymphoma” +1]/365.25.
 
The day of diagnosis should be the first day of the month provided. If the month of diagnosis is unknown, the date of diagnosis should be “January 1st” of the year provided.
										
Mean dose of Adcetris	Is calculated as the total value of each dose of Adcetris given at each treatment cycle divided by the number of cycles.										

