Dose of Adcetris per 3 weeks	
Is calculated using the following formula: Total “dose of Adcetris”/([“date of the last dose of Adcetris” – “date of the initial dose of Adcetris” + 21)/21].
 
If only 1 cycle of treatment is given, the “date of the last dose of Adcetris” and the “date of the initial dose of Adcetris” should be regarded as the same.
										
Degree of decreased neutrophil count at baseline	
The neutrophil count at baseline will be classified as shown in the table below. If the neutrophil count at baseline is missing, the degree of the neutrophil count at baseline should be handled as missing:
 
  
 No decrease	≥2,000 /mm³	
 
 Grade 1	≥1,500 to <2,000 /mm³	
 
 Grade 2	≥1,000 to <1,500 /mm³	
 
 Grade 3	≥500 to <1,000 /mm³	
 
 Grade 4	<500 /mm³	
  
	No decrease	≥2,000 /mm ³	Grade 1	≥1,500 to <2,000 /mm ³	Grade 2	≥1,000 to <1,500 /mm ³	Grade 3	≥500 to <1,000 /mm ³	Grade 4	<500 /mm ³
No decrease	≥2,000 /mm ³										
Grade 1	≥1,500 to <2,000 /mm ³										
Grade 2	≥1,000 to <1,500 /mm ³										
Grade 3	≥500 to <1,000 /mm ³										
Grade 4	<500 /mm ³										
Days from the month of the completion of the final regimen	Is calculated using the following formula: date of the initial dose of Adcetris – date of the completion of the final regimen of prior drug										

Term	Definition
of prior drug therapy to the date of 1 cycle of treatment with Adcetris	therapy + 1. If the month of “the completion of the final regimen of prior drug therapy” is missing, the date of the completion of the final regimen of prior drug therapy should be handled as missing.

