1.3 Level of significance and confidence coefficient

Level of significance: Two-sided 5%

Confidence coefficient: Two-sided 95%

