5.2.4 Occurrence of adverse drug reactions/infections by CTCAE Grade (the worst one)

(1) Analysis sets to be used

Safety analysis set, safety analysis set (Hodgkin’s lymphoma), and safety analysis set (anaplastic large-cell lymphoma)

(2) Data to be analyzed

For each data item, patients will be stratified into the following categories, and the type of adverse drug reactions, etc., will be analyzed:

Data item	Category
CTCAE Grade (the worst one)	≤Grade 2, ≥Grade 3, or unknown

The type of adverse drug reactions, etc., will be analyzed as follows:

Data item	Data to be analyzed
Type of adverse drug reactions, etc.	The incidence of adverse drug reactions, etc., for each CTCAE grade (the worst one) will be calculated by SOC and PT. For SOC, the number and percentage of patients with drug reactions, etc., will be calculated. For PT, the number and percentage of drug reactions, etc., will be calculated. SOCs will be presented in the internationally agreed order, and PTs will be presented in ascending order of HLGT and PT codes if their SOCs are “Investigations,” and in ascending order of PT code otherwise. The CTCAE grade (the worst one) is higher in the order of ≥Grade 3, ≤Grade 2, and unknown. If the same patient has multiple occurrences of the same adverse drug reaction, etc. (PT), the reaction with the highest CTCAE grade will be counted once per patient.

(3) Figure/table number

Tables 5.2.4-1 to 5.2.4-3

5.3 Percentage of patients with adverse drug reactions/infections by patient demographics and baseline characteristics and treatment given

(1) Analysis sets to be used

Safety analysis set, safety analysis set (Hodgkin’s lymphoma), and safety analysis set (anaplastic large-cell lymphoma)

(2) Data to be analyzed

For each data item, patients will be stratified into the following categories, and the percentage of patients with adverse drug reactions, etc. (with point estimate and 95% confidence interval) will be determined.

For categories associated and not associated with ranking, Fisher’s exact and Mann-Whitney U tests, respectively, will be used. If there is a category of “unknown,” it will be excluded to perform

the Mann-Whitney U test.

Data item	Category
Sex	Male or female
Age	<18 years, 18 to 64 years, 65 to 74 years, or ≥ 75 years
Disease duration	<1 year, <1 to 3 years, <3 to 5 years, ≥ 5 years, or unknown
ALK (for patients with anaplastic large-cell lymphoma)	Positive, negative, or unknown
Clinical stage	I, II, III, IV, or unknown

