B symptoms	Absent or present
ECOG Performance Status	0, 1, 2, 3, or 4
Past history of pulmonary disorders	Absent or present
Concurrent pulmonary disorders	Absent or present
Past history of malignant tumours	Absent or present
Concurrent malignant tumours	Absent or present
Concurrent hepatic disorders	Absent or present
Grade of hepatic disorder (Grade based on AST and ALT levels)	None, Grade 1, Grade 2, \geq Grade 3, or unknown
Concurrent renal disorders	Absent or present
Grade of renal disorder (Grade based on serum creatinine)	None, Grade 1, Grade 2, \geq Grade 3, or unknown
Weight	<40 kg, <40 to 50 kg, <50 to 60 kg, <60 to 70 kg, or ≥ 70 kg
BMI	<18.5 kg/m ² , <18.5 to 25 kg/m ² , <25 to 30 kg/m ² , or ≥ 30 kg/m ²
Smoking history	Never, current, past, or unknown
Prior drug therapy	Absent or present
Prior radiotherapy	Absent or present
Prior hematopoietic stem cell transplantation	Absent, present (autologous), present (homologous), present (autologous and homologous), or unknown
Initial dose of Adcetris	<1.2 mg/kg, 1.2 mg/kg, >1.2 mg/kg to <1.8 mg/kg, 1.8 mg/kg, or >1.8 mg/kg

Data item	Category
Mean dose of Adcetris	<1.2 mg/kg, 1.2 mg/kg, >1.2 mg/kg to <1.8 mg/kg, 1.8 mg/kg, or >1.8 mg/kg
Dose of Adcetris per 3 weeks	<1.2 mg/kg, 1.2 mg/kg, >1.2 mg/kg to <1.8 mg/kg, 1.8 mg/kg, or >1.8 mg/kg
Drug(s) other than Adcetris used for the treatment of the primary disease	Absent or present

(3) Figure/table number

Tables 5.3-1 to 5.3-3

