Items and categories of patient demographics and baseline characteristics and treatment given

Data item	Category
Sex	Male or female
Age	<18 years, 18 to 64 years, 65 to 74 years, or ≥75 years
Disease duration	<1 year, <1 to 3 years, <3 to 5years, ≥5 years, or unknown
ECOG Performance Status	0, 1, 2, 3, or 4
Concurrent peripheral nerve disorders	None, Grade 1, Grade 2, Grade 3, Grade 4, or unknown
Weight	<40 kg, <40 to 50 kg, <50 to 60 kg, <60 to 70 kg, or ≥70 kg
Prior ABVD or CHOP	Absent or present
Prior radiotherapy	Absent or present
Prior hematopoietic stem cell transplantation	Absent, present (autologous), present (homologous), present (autologous and homologous), or unknown
Initial dose of Adcetris	<1.2 mg/kg, 1.2 mg/kg, >1.2 mg/kg to <1.8 mg/kg, 1.8 mg/kg, or >1.8 mg/kg
Mean dose of Adcetris	<1.2 mg/kg, 1.2 mg/kg, >1.2 mg/kg to <1.8 mg/kg, 1.8 mg/kg, or >1.8 mg/kg
Dose of Adcetris per 3 weeks	<1.2 mg/kg, 1.2 mg/kg, >1.2 mg/kg to <1.8 mg/kg, 1.8 mg/kg, or >1.8 mg/kg
Concurrent diabetes mellitus	Absent or present

(3) Figure/table number

Tables 5.9.2-1 to 5.9.2-3

5.9.3 Treatment with Adcetris at the onset of peripheral nerve disorders considered related to Adcetris

(1) Analysis sets to be used

Patients included in the safety analysis set and safety analysis set (Hodgkin’s lymphoma) or safety analysis set (anaplastic large-cell lymphoma) who experience peripheral nerve disorders considered related to Adcetris

(2) Data to be analyzed

For each CTCAE Grade (the worst one) of peripheral nerve disorders considered related to Adcetris, patients will be stratified into the categories below, and the incidence of peripheral nerve disorders will be calculated. If the same patient has multiple occurrences of the same peripheral nerve disorder (PT), the total number of occurrences will be calculated per category (for example, if the same patient has one episode of peripheral nerve disorder requiring dose reduction and one episode of peripheral nerve disorder leading to treatment discontinuation, these episodes of peripheral nerve disorder will be counted once for each category). The percentage of peripheral nerve disorders for each category will be calculated using the number of peripheral nerve disorders for each CTCAE grade (the worst one) as the denominator.

For each data item, missing data will be handled as “not provided.”

Data item	Category
Action taken to Adcetris	No action taken or action taken in response to the event or not provided

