Specific action taken to Adcetris	Dose reduction, treatment interruption (treatment delay), treatment discontinuation, or not provided

(3) Figure/table number

Tables 5.9.3-1 to 5.9.3-3

5.9.4 Outcome of peripheral nerve disorders (\geq CTCAE Grade 3) considered related to Adcetris by action taken with Adcetris

(1) Analysis sets to be used

Patients included in safety evaluation and patients included in safety evaluation (Hodgkin’s lymphoma) or patients included in safety evaluation (anaplastic large-cell lymphoma) who experience peripheral nerve disorder (\geq CTCAE Grade 3) considered related to Adcetris

(2) Data to be analyzed

For peripheral nerve disorders considered related to Adcetris, patients will be stratified into the categories below for each outcome and the incidence of these peripheral nerve disorders will be calculated. If the same patient has multiple occurrences of peripheral nerve disorder, the total number of occurrences will be calculated per category (for example, if the same patient has one episode of peripheral nerve disorder requiring dose reduction and one episode of peripheral nerve disorder leading to treatment discontinuation, these episodes of peripheral nerve disorder will be counted once for each category).

For each data item, missing data will be handled as “not provided.” The percentage of peripheral nerve disorders for each category will be calculated using the total number of peripheral nerve

disorders for each category as the denominator:

Data item	Category
Action taken to Adcetris	No action taken or action taken in response to the event or not provided
Specific action taken to Adcetris	Dose reduction, treatment interruption (treatment delay), treatment discontinuation, or not provided

(3) Figure/table number

Tables 5.9.4-1 to 5.9.4-3

5.9.5 Occurrence of infections considered related to Adcetris by presence or absence of drugs used for the prevention of infection

(1) Analysis sets to be used

Safety analysis set, safety analysis set (Hodgkin's lymphoma), and safety analysis set (anaplastic large-cell lymphoma)

(2) Data to be analyzed

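### SAP 5.3 and 5.9.2 group reactions by whole-course dose measures that the reaction itself can change, so a dose-response of either sign can appear when dose has no effect

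*SAP*

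**What the plan says.** The current SAP defines two on-treatment dose measures in the definitions table of Section 1.0. Mean dose "Is calculated as the total value of each dose of Adcetris given at each treatment cycle divided by the number of cycles". Dose per 3 weeks is total dose divided by the number of 21-day periods from the first dose to the "date of the last dose of Adcetris", with 21 days added. Neither definition stops at the onset of a reaction.

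Both measures, with initial dose, are grouping factors in two tables. Each uses five categories built around 1.2 and 1.8 mg/kg.

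- **Section 5.3** (any adverse drug reaction): for each category, "the percentage of patients with adverse drug reactions, etc. (with point estimate and 95% confidence interval) will be determined". Fisher's exact or Mann-Whitney tests follow, and Section 1.3 sets a two-sided 5% level.
- **Section 5.9.2** (related neuropathy by worst grade): incidence is tabulated and no test is stated.

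Elsewhere the documents expect dosing to respond to the event. Protocol 9.2.5, on peripheral nerve disorders, speaks of "continuation of treatment (including dose reduction and restart of treatment after treatment interruption". SAP 5.9.3 tabulates the action taken as "Dose reduction, treatment interruption (treatment delay), treatment discontinuation, or not provided", and its worked example is a patient with "one episode of peripheral nerve disorder requiring dose reduction and one episode of peripheral nerve disorder leading to treatment discontinuation". SAP 4.1 reports treatment length from 1 to 17 or more cycles, with several reasons for stopping.

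Neither 5.3 nor 5.9.2 has a cut-off at onset, a lag, a landmark, an adjustment for number of cycles, or a caution to the reader.

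**The concern.** A grouping factor should be settled before the outcome it is meant to explain. Here it can be settled afterwards, in two ways.

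1. **Response to the reaction.** If a reaction leads to reduction or delay, the patient moves into a lower-dose stratum and lower dose looks more toxic. If it leads to stopping, the patient's dose is frozen at its early level while patients without a reaction continue and collect unrelated reductions and delays. Higher dose then looks more toxic.
2. **Treatment length.** Patients treated longer have more cycles in which to have a reaction and more in which to have an unrelated delay or reduction. This affects dose per 3 weeks when delays or reductions build up over cycles. It affects mean dose only when reductions do.

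Protocol 9.2.5 wants neuropathy risk factors that help patients continue treatment. A dose row whose pattern may be produced by the management of the event works against that aim.

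**Working it through.** **The plan's own figures.** The SAP gives no figure for the dose strata. The only sample-size figure, 140 patients (Protocol 3.2), reproduces: the probability of at least 10 infusion reactions at 11% is 0.952, and 140 is the smallest number that reaches 95%.

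**Arithmetic on the two definitions** (1.2 and 1.8 are used only because they are SAP stratum boundaries):

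- Four cycles at 1.8, a reaction, then twelve at 1.2: (4 × 1.8 + 12 × 1.2) / 16 = 21.6 / 16 = **1.35**. The patient is in the stratum between 1.2 and 1.8, although every dose before the reaction was 1.8.
- The same reaction followed by stopping: 7.2 / 4 = **1.80**.
- Sixteen cycles at 1.8 with one 7-day delay: 28.8 / [(315 + 7 + 21) / 21] = 28.8 / 16.33 = **1.76** per 3 weeks. Mean dose is still 1.80.

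**Simulation with no dose effect.** From the documents: 16 cycles; 56% neuropathy incidence (Protocol 3.2), obtained with 5% onset per cycle because 1 − 0.95^16 = 0.56. Assumed, because the documents give no rates: 2% unrelated reduction and 2% unrelated 7-day delay per cycle; the event-driven rates shown below; changes apply from the next cycle; a calculated value counts as 1.8 only if exactly 1.8. There are 400,000 patients per row. Entries are percent with a reaction, lower-dose stratum vs 1.8 stratum, or the gap alone in points. A positive gap is an inverse dose-response.

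| Assumed pattern | Mean dose | Dose per 3 weeks |
|---|---|---|
| 10% of cases reduced, 10% delayed, none stop | 61.6 vs 53.7 (+8) | 60.8 vs 51.2 (+10) |
| 30% reduced, 30% delayed, none stop | 69.6 vs 47.6 (+22) | 66.8 vs 39.5 (+27) |
| 10% and 10%, 20% of cases stop | +3 | +3 |
| 30% and 30%, 20% stop | +16 | +17 |
| 20% and 20%, 50% stop | 0 | −3 |
| No event-driven change, 50% stop | 48.0 vs 58.2 (−10) | 48.4 vs 60.7 (−12) |
| Length only: 8% unrelated stopping and 7.5% onset per cycle, no event-driven change | +17 | +19 |

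Initial-dose strata under the same scenarios differ by less than 1 point.

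**Dependence on the assumptions.** In the length-only row, without unrelated reductions nobody leaves the 1.8 mean-dose stratum, so that bias disappears. For dose per 3 weeks, rounding to one decimal before classifying cuts the length-only gap from +19 to about +13, and to 2 or 3 points if unrelated reductions are also removed. It moves the −12 to about −6. The 1.76 above shows why: rounded, it falls back into the 1.8 stratum.

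**Test in 5.3.** Illustration with 140 patients, Fisher's exact test on two collapsed strata (below 1.8 vs 1.8), an assumed 80% any-reaction incidence and 2% unrelated change. Chance of p < 0.05 (mean dose; dose per 3 weeks):

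- no event-driven change, no stopping: 4%; 4%
- 10% event-driven change, 20% stopping: 4%; 5%
- no event-driven change, 50% stopping: about 15%; 24%
- 30% event-driven change, none stop: about 50%; 71%

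**The case against.** The strongest reply has five parts.

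- **Mean dose does not depend on length as such.** At a constant dose it is the same after 2 cycles or 16. This stands, and the length mechanism is stated conditionally for that reason.
- **The sizes are soft.** The SAP does not say how a calculated dose per 3 weeks is rounded into the 1.8 category; its Section 1.2 governs display only. This stands, and the second column of the table is the less stable one.
- **The rejection rates are not those of the planned test.** Section 5.3 has five categories, and its sentence matching tests to ranked and unranked factors appears reversed, so the planned test is unclear. The 80% incidence is in neither document, and one moderate pattern rejects at about the nominal rate. This stands. A reader might take 50% or 71% as the false-positive rate of the SAP analysis; the documents do not support that.
- **Other tables help.** Initial dose is in both tables and later events cannot change it. Sections 5.9.3 and 5.9.4 show actions taken, and Table 5.10 lists onset and per-cycle dosing for each related neuropathy case. The event-driven part can therefore be inspected for neuropathy. Table 5.10 has no patients without neuropathy, so it cannot correct the comparison, and 5.3 has no matching listing for all reactions.
- **The stakes are modest.** This is a single-arm surveillance, these are two of 25 unadjusted factors in 5.3, and no decision rule uses them. That limits the severity. It does not justify p-values on a factor that the outcome can alter.

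**Conclusion.** The point holds as a structural flaw that should be corrected. It follows from the SAP's definitions and from the dose changes that both documents anticipate, and it needs no assumed rates.

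The size is not fixed. Under the illustrative assumptions, with no dose effect, the false gap runs from about +27 to −12 points and can be near zero. The documents give no frequency of event-driven reduction, delay or stopping, nor a classification rule for dose per 3 weeks.

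Three stronger readings are tempting and go too far:

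- That these rows will necessarily make lower doses look worse. Enough stopping at the reaction reverses the sign.
- That both measures always track treatment length. Mean dose does so only when reductions accrue.
- That 5.9.2 will produce false significance. It states no test; its risk is a table that misleads. The false-significance risk belongs to 5.3.

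**What to change.** In 5.3 and 5.9.2, show the mean-dose and "Dose of Adcetris per 3 weeks" rows as description only, and remove their tests from 5.3. Add one footnote: dose may have been changed because of the reaction, and the measures can also vary with treatment length when doses are reduced or delayed. Use initial dose for any tested dose comparison, noting that it may be confounded by the baseline factors that SAP 4.3 tabulates against it (age, performance status, and hepatic, renal, infection and neuropathy status). This keeps on-treatment dose in the tables, which suits Protocol 10.4.2, where event frequency is to be examined by treatment given.

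Alternative: drop the two rows from 5.3 and 5.9.2 and leave the measures in Table 4.1, if the sponsor judges initial dose sufficient for Protocol 10.4.2.

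Cost: two p-values lost and one footnote added. No new data are needed.

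Optional: a landmark or time-varying dose analysis of neuropathy, using per-cycle doses for all patients rather than Table 5.10 alone. In a separate simulation with no dose effect, counting only dose accrued up to each cycle at risk and stratifying by cycle brought rejection back to 4.6–6.6%. A landmark loses precision: after Cycle 4, 52% to 81% of patients remained under the assumptions used, about 73 to 113 of 140 (0.52 × 140 and 0.81 × 140). It suits the any-reaction outcome of 5.3 poorly.

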#### 2) When to collect outcome measure data

From the start of treatment with Adcetris until the completion of 16 cycles (or upon discontinuation of treatment with Adcetris)

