Days from the month of the completion of the most recent prior radiotherapy to the date of 1 cycle of treatment with Adcetris	Is calculated using the following formula: date of the initial dose of Adcetris – date of the completion of the most recent prior radiotherapy + 1. If the month of “the completion of the most recent prior radiotherapy” is missing, the date of the completion of the most recent prior radiotherapy should be handled as missing.
Days from the date of the last dose of Adcetris to hematopoietic stem cell transplantation (autologous) (Post-baseline hematopoietic stem cell transplantation: autologous)	For patients with post-baseline hematopoietic stem cell transplantation (autologous), this data item will be calculated using the following formula: date of post-baseline hematopoietic stem cell transplantation (autologous) – date of the last dose of Adcetris + 1. If the date of post-baseline hematopoietic stem cell transplantation (autologous) is missing, this data item should be handled as missing. For patients with no post-baseline hematopoietic stem cell transplantation (autologous), this data item should be handled as missing.
Duration of treatment with Adcetris prior to hematopoietic stem cell transplantation (autologous) (Post-baseline hematopoietic stem cell transplantation: autologous)	For patients with post-baseline hematopoietic stem cell transplantation (autologous), this data item will be calculated using the following formula: date of the last dose of Adcetris – date of the initial dose of Adcetris + 1. If the date of post-baseline hematopoietic stem cell transplantation (autologous) is missing, this data item should be handled as missing. For patients with no post-baseline hematopoietic stem cell transplantation (autologous), this data item should be handled as missing.

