Days from the date of the last dose of Adcetris to hematopoietic stem cell transplantation (homologous) (Post-baseline hematopoietic stem cell transplantation: homologous)	For patients with post-baseline hematopoietic stem cell transplantation (homologous), this data item will be calculated using the following formula: date of hematopoietic stem cell transplantation (homologous) – date of the last dose of Adcetris + 1. If the date of post-baseline hematopoietic stem cell transplantation (homologous) is missing, this data item should be handled as missing. For patients with no post-baseline hematopoietic stem cell transplantation (homologous), this data item should be handled as missing.
Duration of treatment with Adcetris prior to hematopoietic stem cell transplantation (homologous) (Post-baseline hematopoietic stem cell transplantation: stem cell transplantation: homologous)	For patients with post-baseline hematopoietic stem cell transplantation (homologous), this data item will be calculated using the following formula: date of the last dose of Adcetris – date of the initial dose of Adcetris + 1. If the date of post-baseline hematopoietic stem cell transplantation (homologous) is missing, this data item should be handled as missing.

Term	Definition
homologous)	For patients with no post-baseline hematopoietic stem cell transplantation (homologous), this data item should be handled as missing.
Date of the final observation	“Date of the final observation” in the case report form If not provided, the most recent date entered in the case report form should be used.
Summary statistics	Number of patients, mean, standard deviation, minimum, 25th percentile, median, 75th percentile, and maximum.
Overall survival	Time to the date of death from any cause after the date of the initial dose of Adcetris. Surviving patients will be censored on the date of survival confirmation. The date of outcome of an adverse event with “Died/fetal” recorded in the Outcome field will be used as the date of death, and the final observation date will be used as the date of survival confirmation. The overall survival (date of death or survival confirmation) = date of death or survival confirmation – date of the initial dose of Adcetris+1
1 year	One year is defined as 365.25 days.
1 month	One month is defined as 30.4375 days.

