4.0 Treatment Given

4.1 Treatment given

(1) Analysis sets to be used

Safety analysis set, safety analysis set (Hodgkin’s lymphoma), and safety analysis set (anaplastic large-cell lymphoma)

(2) Data to be analyzed

For each data item, patients will be stratified into the following categories below, and the frequency will be calculated. In addition, summary statistics of continuous variable will be calculated:

Data item	Category
Initial dose of Adcetris	<1.2 mg/kg, 1.2 mg/kg, >1.2 mg/kg to <1.8 mg/kg, 1.8 mg/kg, or >1.8 mg/kg
Mean dose of Adcetris	<1.2 mg/kg, 1.2 mg/kg, >1.2 mg/kg to <1.8 mg/kg, 1.8 mg/kg, or >1.8 mg/kg
Dose of Adcetris per 3 weeks	<1.2 mg/kg, 1.2 mg/kg, >1.2 mg/kg to <1.8 mg/kg, 1.8 mg/kg, or >1.8 mg/kg
Duration of treatment with Adcetris	1, 2, 3, 4, 5, 6, 7, 8, 9, 10, 11, 12, 13, 14, 15, 16, or ≥ 17 cycles
Reason(s) for discontinuation of Adcetris	Treatment goal achieved, adverse event(s), lost to follow-up, transfer to another hospital, pregnancy, inadequate response, and/or other
Post-baseline hematopoietic stem cell transplantation	Absent, present, or unknown
Type of post-baseline hematopoietic stem cell transplantation	Autologous or homologous
Days from the date of the last dose of Adcetris to hematopoietic stem cell transplantation (autologous) (Post-baseline hematopoietic stem cell transplantation: autologous)	-
Duration of treatment with Adcetris prior to	-

hematopoietic stem cell transplantation (autologous) (Post-baseline hematopoietic stem cell transplantation: autologous)	
Days from the date of the last dose of Adcetris to hematopoietic stem cell transplantation (homologous) (Post-baseline hematopoietic stem cell transplantation: homologous)	-
Duration of treatment with Adcetris prior to hematopoietic stem cell transplantation (homologous) (Post-baseline hematopoietic stem cell transplantation: homologous)	-
Drug(s) other than Adcetris used for the treatment of the primary disease	Absent or present
Drug(s) used for the prevention of infection	Absent or present
Specific drug(s) used for the prevention of infection	Antibiotics/synthetic antibacterial agents, antifungals, antivirals, trimethoprim-sulfamethoxazole combinations, and/or other prophylactics against infections

(3) Figure/table number

Tables 4.1-1 to 4.1-3

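### The four transplant-timing items use the overall last Adcetris dose, so they give wrong values for any patient dosed again after a transplant (minor; the number affected may be zero)

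*SAP*

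**What the plan says.** The definitions table in SAP Section 1.0 (it follows 1.1.2) has two derived items for each type of post-baseline transplant.

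- **Interval to transplant.** For autologous transplants: "date of post-baseline hematopoietic stem cell transplantation (autologous) – date of the last dose of Adcetris + 1". For homologous transplants: "date of hematopoietic stem cell transplantation (homologous) – date of the last dose of Adcetris + 1".
- **Duration of treatment before transplant.** For both types: "date of the last dose of Adcetris – date of the initial dose of Adcetris + 1". The label of the autologous item begins "Duration of treatment with Adcetris prior to hematopoietic stem cell transplantation (autologous", so it is meant to describe treatment before the transplant, but the transplant date does not appear in the formula.

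The only exceptions are a missing transplant date and no transplant of that type. For the first, the table says: "If the date of post-baseline hematopoietic stem cell transplantation (autologous) is missing, this data item should be handled as missing". Dosing after a transplant is not mentioned. SAP 4.1 reports all four items as summary statistics.

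**The concern.** A formula with an unrestricted last dose is right only if no Adcetris is given after the transplant. The plan does not guarantee that. Observation runs to the end of 16 cycles (Protocol 7.1), transplants are recorded within it (Protocol 9.2.3 and Appendix 1), and nothing ends dosing or observation at a transplant.

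For a patient dosed again, the interval item would be zero or negative. The duration item would be a span in days that takes in the gap around the transplant and the later dosing period. SAP 4.1 is the only place where exposure before a post-baseline transplant, and the interval to that transplant, are summarised. The mean, standard deviation, minimum and maximum would all take in the wrong values.

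**Working it through.** The plan gives no figure to reproduce, so the check applies the formulas as written.

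**Which last dose is meant.** In the same table, the dose per 3 weeks divides the total dose by a span ending at the last-dose date. That date must therefore be the last dose of the whole course. No second meaning is defined for the transplant items.

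**Algebra.** Let I be the first dose, P the latest dose on or before the transplant, T the transplant and L the overall last dose.

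- Interval: SAP T - L + 1; intended T - P + 1; error -(L - P).
- Duration: SAP L - I + 1; intended P - I + 1; error +(L - P).

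If L is on or before T, then L = P and both items are correct. If L = T + 1, the interval is 0; from L = T + 2 it is negative. A correct interval is at least 1, so every affected patient shows an interval of 0 or less. The duration item carries no such signal.

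**Assumed patient.** Doses on days 1, 22, 43 and 64; transplant on day 100. These days are illustrative and do not come from the documents. The intended values are 100 - 64 + 1 = 37 and 64 - 1 + 1 = 64.

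| Dosing after transplant | L | SAP interval | SAP duration |
|---|---|---|---|
| None | 64 | 37 | 64 |
| One dose, day 101 | 101 | 0 | 101 |
| One dose, day 102 | 102 | -1 | 102 |
| One dose, day 160 | 160 | -59 | 160 |
| Four doses, days 160 to 223 | 223 | -122 | 223 |
| Twelve doses from day 160 (16 in all) | 391 | -290 | 391 |

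With P in place of L, every row gives 37 and 64.

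**Effect on a mean (subgroup size also assumed).** Each affected patient among n moves the mean by (L - P)/n.

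- None affected: no change.
- One of ten with the four-dose pattern, the others at 37 and 64: mean interval (9 × 37 - 122)/10 = 21.1 instead of 37.0; mean duration (9 × 64 + 223)/10 = 79.9 instead of 64.0. The shift is 159/10 = 15.9 days each way. The median interval stays at 37.

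**Two transplants.** If both follow the final dose, measuring both from that dose is correct. If doses fall between them, the first transplant's interval and duration are wrong and the second's are right. If doses follow both, all four values are wrong.

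**The case against.** The best defence is that the labels presuppose the order: last dose first, then transplant. For that order the formulas are right, so at most a qualifier is missing. Nor does any text describe dosing after a transplant. Transplant is not a named reason for discontinuation in SAP 4.1, but a stop for transplant could be recorded as treatment goal achieved or as other. A negative minimum would prompt a check, and one outlier hardly moves a median. All this stands, and it limits the severity. It does not make the formulas right for a sequence that the plan allows.

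A reader might infer more from three places, and should not.

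- **Restart after interruption.** Protocol 9.2.5 mentions "dose reduction and restart of treatment after treatment interruption", but in the rationale for following peripheral nerve disorders and neutropenia. It says nothing about dosing after a transplant.
- **Collection window.** Protocol 9.2.3 collects treatment data "From the start of treatment with Adcetris until the completion of 16 cycles (or upon discontinuation of treatment with Adcetris"). It is tempting to conclude that recorded transplants must include some done during an interruption. Appendix 1 also marks transplant for collection upon discontinuation, and Protocol 7.4 allows the form to be completed within 1 month after the required observation. A transplant soon after stopping, which the formulas handle correctly, can therefore be recorded too.
- **Two transplants.** A shared last dose is not an error in itself. The SAP's combined autologous and homologous category concerns prior transplants. Nothing rules out both after baseline, but nothing shows it either.

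**Conclusion.** The point holds as a minor defect of definition. The stated rule gives wrong values in all four items whenever the overall last dose falls after the transplant concerned. The error is exactly the number of days between the latest pre-transplant dose and the overall last dose, subtracted from the interval and added to the duration.

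The number of affected patients is unknown and may be zero, in which case the reported summaries are correct as they stand. The day counts and the subgroup of ten are assumptions that show the mechanism; they do not estimate its effect in this study. The items are descriptive. No test, survival estimate or analysis of an event of particular interest uses them.

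**What to change.** In all four definitions, replace the overall last-dose date with the date of the latest Adcetris dose given on or before that transplantation, applied separately to each transplant. The missing-date rule for the duration items then also makes sense, because the derivation will actually need the transplant date.

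The cost is a few words in the definitions table and a small programming change. No new data are needed: dose dates by cycle are available (they are listed in SAP 5.10 and 5.11) and transplant dates are collected under Protocol 9.2.3. Reporting how many patients were dosed again after a transplant is optional; it would show whether the change affected any value.
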